For each treatment arm, treatment-emergent AE's, SAEs, SADEs, ADEs, USADEs and DDs will be summarised by organ system and treatment causality. The number and percentage of patients discontinuing the study due to Aes, SAEs, SADEs or other stopping criteria confirmed by the Data Safety Monitoring Board (DSMB) will be summarized for each arm. Secondary and exploratory parameters (changes from baseline at each study visit) will be descriptively analysed by treatment arm by means of the appropriate statistics.

Statistical analyses of safety data will be run when each study cohort is completed and the corresponding results will be communicated to the DSMB. Data extraction at interim time points do not serve study analyses.

Number of Visits

Patients will undergo the following

Screening assessment (up to 72hrs)6

Study Day 0-randomisation (DIALIVE treatment may commence on this day if all day 1

parameters have been met) Study Day 1 assessments7

Study Days 1-10 treatment phase commences and completes

Study Day 5 assessments

Study Day 10 assessments

Study Day 14 assessments

Study Day 28 assessments

Study Day 90 assessments

One treatment will be defined as any duration of exposure to the DIALIVE.

Viral serology results from up to 8 weeks before the screening period will be accepted

⁶ Screening period (post consent) has been set up to 72 hours to allow sufficient time to gather all relevant clinical information for the subject to be eligible to progress to randomisation. However, if this information becomes available sooner, then randomisation can proceed after that time (without having to wait for 72 hours). For further clarity, the plan for gathering the most recent and relevant clinical information, yet not delaying the start of the study is as follows:

a. Thorough clinical examination of the patient and assessment of FBC, U&E, LFT, Coagulation must be repeated during this period. If randomised to the DIALIVE arm FBC, U&E, LFT, Coagulation results from the screening period may be used if performed up to 24 hours prior to starting treatment unless patients' clinical status has changed.

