5.1.6. Equipment to be used for assessing the clinical investigation

All equipment except for the DIALIVE device, the EAA luminometer for endotoxin analysis, and the Primsmaflex platform¹¹ will be the property of the Investigator(s) and/or institutions and maintained and calibrated according to institutional guidelines. Records of maintenance and calibration will be made available at the Sponsor's request.

5.1.7. Replacement of subjects.

30 evaluable patients will be recruited across all sites to receive either treatment using the DIALIVE or SOC. Screen failures will be replaced to achieve an even balance in each cohort. The patient numbers will be increased and replaced if there are dropouts during the treatment period to allow 30 evaluable patients to be included. Dropouts can be i) patients who withdraw their consent, ii) patients who are considered 'not evaluable' because of an incomplete dialysis cycle (for DIALIVE patients) or iii) if a patient dies in the 10-day period following randomization to the SOC-arm, or iv) patients who are excluded based on a stopping rule.

A dropout rate of 17% is anticipated on the basis of observations made during execution of this study in the first 2 cohorts of patients. Patients who drop-out for reasons of an incomplete dialysis cycle are followed up for a duration of 28 days post-randomization.

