6. STATISTICAL CONSIDERATIONS

An independent statistician will be responsible for all statistical aspects of the investigation.

All statistical analyses will be carried out on the safety population, defined as the subset of randomised patients who receive at least one treatment. No imputation of missing values will be implemented. Only available data will be analysed. In addition, a sensitivity analysis will be carried out to check the main safety results using SAE-data of all evaluable patients, defined as all those patients who received standard of care or those who received the correct dialysis treatment cycle.

Due to the nature of the study all statistical analyses will be descriptive. The categorical variables will be summarised by means of the count and percentages corresponding to each variable category, while continuous variable will be summarised by the mean and Standard Deviation of each distribution or the median and min-max values in case of those variables non-normally distributed.

Clinical Investigation Plan CIP YAQ-002 Version: 7.0 10 October 20	19
--	----

For each treatment arm, treatment-emergent AEs, SAEs, SADEs, ADEs, USADEs and DDs will be summarised by organ system and treatment causality. The number and percentage of patients discontinuing the study due to AEs, SAEs, SADEs or other stopping criteria confirmed by the DSMB (withdrawal of patient consent; development of septic shock; progression to ACLF Grade 3b or more; disseminated Intravascular coagulation; unanticipated serious adverse device effects, device deficiencies, or in the opinion of the PI, the treatment is unsafe to continue) will be summarised by treatment arm.

Secondary and exploratory parameters (changes from baseline at each study visit) will be descriptively analysed by treatment arm by means of the appropriate statistics.

Statistical analyses of safety data will be run when each study cohort is completed (minimally one week FU) and the corresponding results will be communicated to the DSMB.

Special interim data extraction required to comply with the EU ALIVER program.

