Appendix 1a- Acute-on-Chronic Liver Failure Grading Scheme per CLIF-OF scoring system.

Grade	Subgroups	ACLF grade equivalent (for DIALIVE study)
No ACLF*	 Patients with no organ failure Patients with a single hepatic, coagulation, circulation or respiratory failure, no AKI and no HE serum creatinine <1.5mg/dL and no hepatic encephalopathy (HE) Patients with single cerebral failure and serum creatinine <1.5mg/dL 	
Grade 1	 Patients with renal failure (sCr > 2 mg/dL) Patients with other single failure organ failure with serum creatinine ≥1.5 and <2 mg/dl and/or HE grade 1-2 	 Patients with serum bilirubin > 20 mg/dL (364 μmol/L) AKI stage 1b (sCr > 1.5 mg/dL or 134 μmol/L)
Grade 2	Patients with 2 organ failures	
Grade 3 a	Patients with 3 organ failures	
Grade 3 b	Patisents with more than 3 organ failure	

From: Moreau, R., et al., *Acute-on-chronic liver failure is a distinct syndrome that develops in patients with acute decompensation of cirrhosis.* Gastroenterology, 2013. **144**(7): p. 1426-37, 1437 e1-9.

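### Section 6's available-data rule makes every ACLF grade, CLIF-C ACLF score and organ-function summary after a death a survivor-only figure

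*Protocol*

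**What the plan says.** Protocol section 6 (repeated in the synopsis) sets the missing-data rule: "No imputation of missing values will be implemented. Only available data will be analysed". On how the endpoints are summarised, it says: "Secondary and exploratory parameters (changes from baseline at each study visit) will be descriptively analysed by treatment arm".

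The population is also fixed there: "All statistical analyses will be carried out on the safety population, defined as the subset of randomised patients who receive at least one treatment". A synopsis footnote counts any "duration of exposure to the DIALIVE" as one treatment, so a DIALIVE patient who dies during or soon after the first session belongs to this population.

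Section 5.1.3 lists change in ACLF grade, change in CLIF-ACLF score and improvement in individual organ function among the secondary endpoints. Mortality at 28 and 90 days is a separate item in the same list. The schedules in section 5.4 place the grade and score at visits up to Day 28 in both arms.

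The highest grade in Appendix 1a, grade 3b, reads "Patisents with more than 3 organ failure". The CLIF-C formulas in Appendix 1b are built from organ scores, age and laboratory values. Neither appendix has a category or value for death.

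Section 6 names one sensitivity analysis: "a sensitivity analysis will be carried out to check the main safety results using SAE-data of all evaluable patients".

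**The concern.** A change from baseline at a visit exists only for a patient who was alive and measured at that visit. If only available data are analysed, and the scale has no level for death, a patient who dies simply disappears from the denominator of all later tables. The worst outcome is removed instead of being counted as the worst outcome.

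Section 4.1 makes clinical benefit of DIALIVE plus standard of care (SOC) over SOC alone a secondary objective, and the grade, score and organ-function summaries serve it. Section 4.2 says randomisation is used to obtain unbiased data in balanced arms. A summary restricted to survivors no longer compares the groups as randomised, because survival itself may depend on treatment. If one arm loses more patients to death, its remaining patients may look better for that reason alone. The reader of a grade or score table would not see this from the table.

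**Working it through.** **Inputs**
- Design: 5 cohorts of 6 patients (section 5.2). 5 × 6 = 30 evaluable patients, 15 per arm, which reproduces the figure in section 5.3.7.
- First two cohorts (Appendix 7 B): 14 enrolled, 8 DIALIVE and 6 SOC. Two DIALIVE patients died 24 to 36 hours after treatment began. No SOC death count is given.
- 28-day mortality cited in section 2.7: 22% for grade 1, 32% for grade 2, 78% for grade 3.
- Dropout (section 5.1.7): "A dropout rate of 17% is anticipated on the basis of observations made during execution of this study in the first 2 cohorts".

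**Step 1. What has already happened.** The first session must start before the end of Day 1 (section 2.2), so a death 24 to 36 hours later falls before Day 5. Both patients are in the safety population, and neither can have a value at Day 5 or later. At most 8 − 2 = 6 of 8 can. If k of the 8 improve, the available-data share is k/6 and the share of all treated is k/8. The ratio is 8/6 = 1.33 whatever k is. For example, k = 1 gives 16.7% against 12.5%.

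**Step 2. Expected loss by Day 28.** Assume that the grade 1 and 2 rates apply. The share with no Day 28 value because of death is then 22% to 32%.
- Per 15 patients: 15 × 0.22 = 3.3 deaths (11.7 left); 15 × 0.32 = 4.8 deaths (10.2 left).
- The binomial probability of at least 3 deaths in an arm of 15 is 67% at 22% mortality and 90% at 32%.
- Dropouts are replaced, so more than 30 patients are enrolled. The stated 17% matches 2/12 = 16.7% (per evaluable patient), whereas 2/14 = 14.3%. On that base the total is 30 × 14/12 = 35. Reading 17% as a share of those enrolled gives 30/0.83 = 36.1, or 37 rounded up. Over this range the expected number without a Day 28 value runs from 35 × 0.22 = 7.7 to 37 × 0.32 = 11.8, so about 8 to 12 patients over both arms.

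**Step 3. When this affects the comparison.** With a share m dead, the available-data percentage equals the all-patient percentage times 1/(1 − m): 1/0.78 = 1.28 and 1/0.68 = 1.47. If m is equal in both arms, the factor is common and the ratio between arms is unchanged. Distortion needs unequal deaths. An illustration with assumed counts, 15 per arm and 6 improved in each arm:

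| Deaths, arm A v arm B | Available data, A | Available data, B | All 15 as denominator, each arm |
|---|---|---|---|
| 5 v 5 | 6/10 = 60.0% | 6/10 = 60.0% | 6/15 = 40.0% |
| 3 v 5 | 6/12 = 50.0% | 6/10 = 60.0% | 6/15 = 40.0% |
| 2 v 5 | 6/13 = 46.2% | 6/10 = 60.0% | 6/15 = 40.0% |

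In the last two rows the arm with more deaths looks better, although the same number improved in each arm.

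**Step 4. Does another planned analysis repair this?** The sensitivity analysis in section 6 is confined to SAE data. The mortality table shows the deaths but leaves the denominators of the grade, score and organ-function tables unchanged.

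**The case against.** The strongest reply is that section 6 does not forbid a death category. It leaves secondary parameters to appropriate descriptive statistics, and a 'dead' row imputes nothing, so an analysis plan could add one without contradicting the protocol. That is true, and it is why the fix is cheap. But the plain reading of change from baseline on available data leaves the dead out, and an analysis plan that follows that text reproduces the problem.

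Second, no distortion between arms is demonstrated. This stands. Appendix 7 B gives no SOC death count, the inflation factor cancels when mortality is equal, and the counts in the illustration are assumed.

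Third, this is a first-in-man safety study without hypothesis tests. Mortality is a separate endpoint, all deaths are reported as SAEs (section 12.4.1), and with so few patients the deaths will be visible. This limits the importance, but it does not correct the tables.

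Two stronger readings are tempting and are not supported:
- A reader might infer that the same rule counts an early death as a short ICU or hospital stay. A stay that ends in death is an observed duration, so a rule about missing values does not govern it. The protocol does not say how such stays are handled, and that detail can be left to the analysis plan. If they were counted to the day of death, the figure would include the dead and would not be survivor-only.
- A reader might infer that the replacement rule in section 5.1.7, which treats it as a dropout "if a patient dies in the 10-day period following randomization to the SOC-arm", also removes patients from these tables. Replacement defines the evaluable set. The tables discussed here use the safety population, and section 5.1.5 keeps all treated subjects in the analyses.

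**Conclusion.** The point holds for ACLF grade, CLIF-C ACLF score and organ function at visits after a death. Values recorded before death still enter the earlier visits. Under the stated rule, the later summaries describe survivors, and at least two of the first 8 DIALIVE patients are already outside them from Day 5. By Day 28 the loss would be 22% to 32% of patients. This assumes that the cited rates for grades 1 and 2 apply and that SOC patients are counted in the analysis population. Grade 3a, stage 1b kidney injury and high-bilirubin entrants change the mix, and the cited rate for grade 3 is much higher.

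The effect on the comparison between arms is a possibility that depends on unequal deaths. Its direction and size cannot be derived from the protocol. With secondary, descriptive endpoints and separate mortality reporting, this is an inexpensive improvement of modest importance and not a flaw in the primary safety evaluation.

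**What to change.** Add to section 6:
- Tabulate ACLF grade at each visit, by arm, for all patients in the analysis population, with 'dead' as the worst category. This records an observed outcome, so it is consistent with the no-imputation rule.
- Beside the available-data summaries of CLIF-C ACLF score and organ function, show the numbers alive, dead and missing at each visit in each arm, and label those summaries as survivor-only.

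Optionally, report days alive and out of ICU and out of hospital to Day 28 next to length of stay.

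The cost is a few sentences and a few tables. No new visits or data items are needed, because grade and score are already scheduled to Day 28 in both arms and deaths are already collected. One drawback is that the grade table mixes death with organ function, so the available-data tables should stay beside it.

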Patients presenting with, or developing during the study period, severe actue renal failure requiring renal support, will receive continuous renal replacement therapy (CRRT) as per standard local practices. This would apply to subjects in both SOC and DIALIVE arms. For those in the DIALIVE arm, the same vascular catheter which is used for DIALIVE treatment may be used for CRRT following the completion of the DIALIVE treatment session. It is however envisaged

that increased intensity of dialysis component in the DIALIVE system (from 1lit/hr to 1.5lit/hr) and allowance for fluid removal in the new protocol may delay or remove altogether the need for CRRTin these situations. The decision for additional CRRT would depend on clinical situation and will be taken by the site PI.

DIALIVE arm consists of standard of care (defined above), plus DIALIVE treatment.

A DIALIVE treatment session denotes treatment for the day, whereas A DIALIVE treatment cycle refers to the total number of treatment days.

A DIALIVE treatment **session** = A minimum, cumulative duration of 8 to 10 hrs (± 30 min) of the DIALIVE treatment, thus allowing for breaks which may be planned (for example patients needing to go for imaging) or unplanned (device clotting, issues with vascular access or other any other unplanned reasons). A break within a treatment session (consisting of a cumulative time longer than 4hrs), or a cumulative duration of less than 8 hrs of dialysis during one day constitutes a session failure for that day. A session failure will require to restart the dialysis session within 24 hrs after the end of the previous session and will reset the start of the dialysis cycle.

A DIALIVE treatment **cycle**= Consists of 3 consecutive days of 8-10 hrs of DIALIVE treatment sessions on each day within the 10 day window period. A break of more than 24hrs between each treatment session will require a new baseline (i.e. a new treatment cycle commenced). A second failed treatment session within the 10 day window period would result in patient exlusion. The patient must have completed one successful treatment cycle within the 10 day window period to be considered evaluable.

Day of randomization constitutes study Day 0.

The first treatment session (DIALIVE arm only) must commence before the end of study Day 1. As such, dialysis might also start on the day of randomization which might created confusion as 'the first day of dialysis' then concurs with DAY 0 of the study schedule.

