5.1.2 Primary Endpoints

The goal is to evaluate the percentage of subjects who experience at least one (1) serious adverse event (SAE) between study Day 1 and Day 10; especially the incidence rate of SAE between the study groups occurring in the period of Day 1 to Day 10.

The percentage of subjects who discontinued DIALIVE due to a serious adverse device event (SADE) between Day 1 (first day of treatment) and Day 10 (DIALIVE arm only)¹⁰.

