5.3.3. Criteria and procedures for subject withdrawal or discontinuation

Other than those required for liver dialysis, no additional Investigation or interventions are expected over and above the routine SOC, which the patient will continue to receive. It is anticipated, therefore, that all subjects will continue to be highly compliant with the CIP study procedures. Non-compliance with the CIP study procedures will be documented by the investigator and reported to the Sponsor as agreed. Persistent non-compliance may lead to be withdrawn of the patient from the study.

The participant may, however, voluntarily choose to withdraw from the study at any time for any reason. This will not in any way affect their routine care. If the participant loses capacity during the study, the legal representative (if appointed) also has the right to withdraw the participant in this instance, acting on the presumed wishes of the participant.

The investigator also has the right to withdraw a patient at any time due to failure to follow CIP, administrative, safety or other reason. Stopping rules (for the study and for the DIALIVE treatment) have been developed as follows:

- A) Rules for discontinuing DIALIVE therapy during a treatment session, based on safety grounds
 - a. Persistent shock (MAP < 65mmHg or < 90% pre-treatment value, whichever is higher) for > 2 hrs with features of tissue hypoperfusion, unresposive to volume resuscitation and/or low dose noradrenaline (0.1µg/kg/min). Treatment can be restarted once haemodynamic stability is restored.
 - b. Deteriorating respiratory failure as defined by worsening PaO₂/FiO₂ to < 200 mmHg (27 kPa) and SaO₂/FiO₂ to < 214. Treatment can be recommenced following a 12 hour recovery period.
 - c. Disseminated Intravascular Coagulation (DIC). Thrombocytopenia alone (to below exclusion criterion threshold) without evidence of DIC is not a stopping rule. Platelet treatment should be considered in this case.
 - d. Progression to more than 3 organ failures

Clinical Investigation Plan CIP YAQ-002 Version: 7.0 10 October 20	19
--	----

- e. In the opinion of the PI, the treatment is unsafe to continue
- B) Study stopping rules for patients randomized to either the SOC or the DIALIVE arm
 - a. Withdrawal of patient consent by the patient (or if applicable the appointed respresentative, where the patient were to lose capacity during this process).

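### The check on the main safety result keeps every SOC patient but only those DIALIVE patients who completed a treatment cycle

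*Protocol*

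**What the plan says.** Section 6 places the main analysis on the safety population, meaning randomised patients with at least one treatment. It then adds a sensitivity analysis "to check the main safety results using SAE-data of all evaluable patients", a set "defined as all those patients who received standard of care or those who received the correct dialysis treatment cycle".

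Section 2.2 gives the condition for the DIALIVE arm: "The patient must have completed one successful treatment cycle within the 10 day window period to be considered evaluable". A cycle is three consecutive days of sessions. One failed session resets the cycle, but "A second failed treatment session within the 10 day window period would result in patient exlusion" (spelling as in the protocol). Section 5.3.3 lets some patients resume after a session is stopped for persistent shock: "Treatment can be restarted once haemodynamic stability is restored".

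The first primary endpoint in Section 5.1.2 is the "percentage of subjects who experience at least one (1) serious adverse event (SAE) between study Day 1 and Day 10". Section 12.4.1 makes every death an SAE.

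Section 5.1.7 lists the dropouts who are replaced until there are 30 evaluable patients. Item (ii) is "patients who are considered 'not evaluable' because of an incomplete dialysis cycle (for DIALIVE patients"). Item (iii), listed separately, applies "if a patient dies in the 10-day period following randomization to the SOC-arm".

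**The concern.** The check filters one arm on something that happens after randomisation and during the endpoint window. A DIALIVE patient who dies on the second day of treatment cannot complete a cycle and leaves the check. A SOC patient who dies on the same day received standard of care and stays. The comparison is then between DIALIVE patients selected for getting through treatment and unselected SOC patients.

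A sensitivity analysis should tell the reader whether the main result survives a reasonable change of assumption. Here a change in the DIALIVE percentage could come from who was removed, and an unchanged percentage could come from removals that happen to cancel. Because the trial is descriptive and runs no tests, readers rely on the percentages themselves.

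A smaller point is that 'evaluable' is used in two ways for early SOC deaths. Section 6 includes them. Section 5.1.7 replaces them so that 30 evaluable patients can be reached, which implies that they do not count.

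**Working it through.** **Who is in which set** (SOC patients are taken to belong to the main set, as a comparison between arms requires)

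| Patient | Main analysis | Section 6 check |
|---|---|---|
| DIALIVE, dies or stops for good before completing a cycle | in | out |
| DIALIVE, second failed session, no completed cycle | in | out |
| DIALIVE, session stopped or failed once, cycle completed later | in | in, SAE counted |
| DIALIVE, non-completer without an SAE (e.g. clotting, access problems) | in | out |
| SOC, dies within 10 days | in | in under Section 6; replaced under 5.1.7(iii) |

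Rows 1 and 4 pull the DIALIVE SAE percentage in opposite directions, so the net shift has no fixed sign.

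**The plan's own figures.** Five cohorts of six give 5 × 6 = 30 evaluable, 15 per arm. Section 5.1.7 anticipates 17% dropout from the first two cohorts. Appendix 7 B reports 14 enrolled (8 DIALIVE, 6 SOC) with 2 DIALIVE patients non-evaluable. The 17% matches 2/12 = 16.7% (per evaluable patient); per enrolled patient it is 2/14 = 14.3%. Within DIALIVE it is 2/8 = 25.0%. No non-evaluable SOC patient is reported.

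**Early deaths in cohorts 1 and 2.** Appendix 7 B reports two DIALIVE deaths 24 to 36 hours after treatment began. It does not say that these are the two non-evaluable patients. The timing, set against a multi-day cycle, and the count (8 − 2 = 6, two cohorts of 3) point that way. If they are the same two:

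- treated patients: 2/8 = 25% (exact 95% CI 3.2% to 65.1%)
- evaluable set: 0/6 = 0% (exact 95% CI 0% to 45.9%)

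**How many patients could leave the check.** Treated DIALIVE patients needed for 15 evaluable = 15/(1 − q), where q is the non-completion rate, assumed to continue:

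- q = 14.3%: 17.5 treated, 2.5 outside the check
- q = 17%: 18.1 treated, 3.1 outside
- q = 25%: 20 treated, 5 outside

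**Effect on the any-SAE percentage (illustration).** The protocol gives no SAE rate, so take an assumed main result of 50%. With k of the removed patients having an SAE:

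- 20 treated, 5 removed: check = (10 − k)/15. For k = 0, 1, 2, 3, 4, 5 this is 66.7%, 60.0%, 53.3%, 46.7%, 40.0%, 33.3%, so up to 17 points either way.
- 18 treated, 3 removed: check = (9 − k)/15, from 60.0% (k = 0) to 40.0% (k = 3), so up to 10 points either way.

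The shift is zero when the removed patients have the same SAE rate s as the arm. Each early death is then offset by (1 − s)/s SAE-free non-completers: 1.5, 1.0 and 0.67 at s = 40%, 50% and 60%.

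**Early SOC deaths (illustration, assumed counts).** With 2 SOC deaths within 10 days and 6 other SOC patients with an SAE, Section 6 gives 8/17 = 47.1%. Leaving the deaths out would give 6/15 = 40.0%.

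**The case against.** The case for leaving the plan alone is that little rests on this set. The main analysis is on treated patients, no hypothesis is tested, and no continuation rule is tied to evaluable patients. Section 5.1.5 requires all SAEs to be reported in full detail and Section 6 tabulates discontinuations by arm, so the removed patients' events can largely be traced. Because any duration of exposure counts as a treatment, a full-exposure table has some use as a completer view. These points stand. They limit the consequence, but they do not turn a set selected in one arm into a test of robustness.

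Three stronger readings are tempting, and the protocol does not support them.

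- **That the check must favour DIALIVE.** This would need the removed patients to have SAEs more often than the arm as a whole. SAE-free non-completers also leave, and patients who resume and complete a cycle stay with their SAE counted.
- **That early SOC deaths are dropped from the safety analysis.** Section 5.1.7 is a replacement rule and attaches 'not evaluable' only to item (ii). It does not override the explicit set in Section 6.
- **That 25% non-completion will persist.** The 2/8 arose under an earlier cycle definition (the amendment history records a change to three sessions of 8 to 10 hours), and Appendix 7 B reports a very stable course in the three DIALIVE patients treated after new guidance was issued.

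The obvious replacement has a weakness of its own. A table of all randomised patients includes DIALIVE patients never connected to the device, which can dilute a device-related SAE rate. It should therefore stand beside the treated-patient table and not replace it.

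**Conclusion.** The point holds and should be fixed. It is confined to the sensitivity analysis. As written, that analysis conditions DIALIVE but not SOC on completing a cycle, within essentially the same ten days as the SAE endpoint, so it cannot show that the main safety result is robust.

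The documented scale is 2 of 8 DIALIVE patients outside the set in cohorts 1 and 2. If these are the two early deaths, which is inferred and not stated, the evaluable set turns 2/8 into 0/6. Both intervals are wide, and the contrast concerns deaths, not the any-SAE endpoint. For that endpoint, the shift of up to 10 to 17 points in either direction depends on an assumed 50% SAE rate and on non-completion continuing at 17% to 25%. The one-sided selection itself rests on no assumption: it follows from Sections 2.2 and 6.

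The mismatch over early SOC deaths is secondary and needs one clarifying sentence.

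**What to change.** 1. **Section 6.** Run the SAE sensitivity analysis on all randomised patients, by arm as first randomised, each counted once, with data up to any withdrawal of consent. Counting by first randomisation matters because Section 2.2 lets a DIALIVE patient who did not start in time re-enter the study. Show the table beside the main treated-patient table and state how many DIALIVE patients were never connected to the device.
2. **Use of 'evaluable'.** Keep it for replacement counts and the performance endpoints (endotoxin and the HNA-2/HMA ratio). If an evaluable SAE table is kept, label it a descriptive completer table and list the deaths and SAEs of the patients left out.
3. **Section 5.1.7.** State that replacement is for recruitment counting only and that replaced patients who were randomised, including those who died, stay in the safety analyses.

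The cost is one more table and a few sentences. Sections 2.2 and 5.1.7 already require 28 days of follow-up for excluded, screen-failed and incomplete-cycle patients, so the SAE data should exist. The DIALIVE figure in the check may become less favourable.
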